# Tracking Physical Activity for Chronic Pain Management Among Older Adults in Detroit

## A. Background and Rationale

Improving function by increasing daily activity is a key goal of cognitive behavioral therapy (CBT) for pain. Incorporating wearable physical activity monitors into the design of cognitive behavioral pain self-management programs provides just-in-time data on patient progress that can be used to individualize behavioral messages and inform goal-setting. The 2016 National Pain Strategy encourages the use of wearable monitors as a pain self-management tool. Activity monitoring is likely to be most convenient for older adults when they can use accessible, commercial-grade monitors and cell phones. However, much remains unknown about how best to integrate these devices into behavioral interventions for specific groups of vulnerable older adults.

The goal of this study is to collect preliminary data regarding wearable monitor use by primarily African American older adults in Detroit in preparation for a trial of a community-based CBT intervention for chronic pain. Findings from the proposed study will inform the design of this future intervention, helping to ensure that it is effective and feasible in the Detroit community setting, and establishing a strong foundation for future competitive proposals. This is a high-priority population given the sharply disproportionate disease burden among older adults in Detroit and race disparities in pain treatment. Facilitators and barriers to activity monitor use in this population will be assessed and the feasibility and validity of various strategies for reporting daily step count data will be tested. This study is also known as the **STEPS (Seniors Tracking Exercise for Pain Self-management)**

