## B. Specific Aims:

1. Identify 50 adults, predominantly African American, age > 60 years with chronic musculoskeletal pain. Thirty of these participants will be randomly assigned to receive a FitBit Zip™ and instructions for reporting daily step-count data in 3 ways (2 weeks each of manual via Interactive Voice Response (IVR) telephone calls, manual via SMS (text messaging), automatic (via syncing the device with an app) (n=30); or to a control group (n=20).
2. After a six-week monitoring period: a) compare step data collection adherence (days provided/days anticipated) among the three intervention modes, within and across subjects; b) assess the validity of manual step reports by comparing them with device-stored data; and c) compare changes in functional outcomes between monitoring and control groups.

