## C. Methods

*Inclusion criteria:* Age  $\geq$  60 years, ambulatory with or without assistive device, community living; have a SMS-capable cell phone, Internet access (via smartphone, in-home or elsewhere); self-reported chronic musculoskeletal pain (pain in muscles or joints for  $\geq$  3 months);  $\geq$ 4 (1-10 scale) average pain level over last week;  $\geq$ 1 day/previous 30 when pain made it difficult to do usual activities. In addition, participants will have to be able to travel to a location in Detroit for a one-time study orientation session.

*Exclusion criteria:* serious acute illness or hospitalization in last month, planned surgery in next month or severe cognitive impairment.

*Recruitment strategies:* A total of 50 adults meeting above eligibility criteria will be recruited from the Healthier Black Elders Center Participant Resource Pool, an opt-in research registry available to UM researchers via the Pepper Center collaboration with Wayne State University. As of January 2017, the database included 1400 individuals with an arthritis diagnosis; many of these registrants are expected to meet pain-related study criteria. Secondary sources will include flyers and outreach at community locations serving Detroit seniors.

*Randomization and data collection:* After completing a baseline telephone survey, participants will be randomly allocated in a 2:1 ratio (intervention: control) using a computer-generated scheme to the monitoring condition or a no-monitoring control group. Participants in the intervention (monitoring) group will be invited to attend an orientation session in a central Detroit location where they will receive a FitBit Zip™ monitor and instructions in setting up their device and reporting data. A project hotline will be available for technical support. Participants will receive \$10 for each questionnaire completed and can keep FitBits upon study completion (control participants will receive FitBits after follow-up survey).

Participants will be asked on the follow-up survey whether they would like to be contacted in the future to learn about opportunities to participate in studies on this topic. They will be told that they will receive all current study incentives whether or not they wish to be contacted in the future, and that they can remove themselves from the “contact” list at any time.

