#### *Functional outcomes*

Per the recommended scoring algorithm (see <https://www.healthmeasures.net/explore-measurement-systems/promis>), items in each PROMIS-29 subscale of Pain Interference, Physical Function, and Social Participation were summed and converted to a subscale T score, a standardized score with a population average of 50 and a standard deviation of 10. Means at baseline and follow-up of each subscale per treatment condition will be calculated.

Repeated measures analysis of variance (ANOVA) will be used to assess treatment effect: A time-by-treatment interaction term, indicating differential pre–post change by group, was the main predictor of interest.

We used chi-square tests to evaluate differences in the proportion of participants in intervention vs control groups who achieved the minimally important difference—that is, the smallest clinically relevant difference—of 3 T-score points in the PROMIS Pain Interference measure and in the proportion who increased the frequency and duration of their low-intensity walks from baseline to follow-up (vs decreased or stayed the same).

Qualitative data on satisfaction, barriers, and facilitators from open-ended survey responses will be compiled and detailed notes made from recordings of postprogram interviews and technical support logs. These were reviewed and coded, and all meaningful statements were placed by two researchers ([name]) into conceptual categories under the broad a priori themes of challenges/disadvantages and facilitators/advantages. In place of specialized software for qualitative analysis, we used standard word processing and spreadsheet apps.

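### Walking is compared between arms only as increased versus not increased; a baseline-adjusted full-scale analysis would make better use of the same answers

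*Combined protocol and SAP*

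**What the plan says.** The walking analysis is in the Functional outcomes part of the Statistical Analysis Plan. One sentence covers two binary comparisons: "We used chi-square tests to evaluate differences in the proportion of participants in intervention vs control groups" who reached a 3-point difference in PROMIS Pain Interference, and then "in the proportion who increased the frequency and duration of their low-intensity walks from baseline to follow-up (vs decreased or stayed the same".

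The two halves are not treated alike. Pain Interference is cut at a stated minimally important difference. It also has T-score means by arm and, on the natural reading, the model introduced by "Repeated measures analysis of variance (ANOVA) will be used to assess treatment effect". That model follows the PROMIS scoring text and does not name walking. Walking has only the cut.

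Elsewhere, section C (Methods) says controls do not track steps, so device data cannot compare activity between arms. It lists physical activity only among the other baseline measures, with no instrument, units or response format. Walking is neither a primary nor a secondary outcome. Aim 2c is to "compare changes in functional outcomes between monitoring and control groups". The Background states that "Improving function by increasing daily activity is a key goal of cognitive behavioral therapy (CBT) for pain".

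**The concern.** If walk frequency and duration are recorded on a graded scale, the cut throws information away. A trivial rise counts the same as a large one. A fall counts the same as no change, so a shift from falling to holding steady is invisible. A participant already in the top category at baseline can never count as a success. The documents offer no threshold rationale for any increase.

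With about 50 participants there is little information to spare, and no other activity measure is compared between arms. The study is meant to inform a later trial. A chi-square p-value on any increase tells its designers little about how much walking changed.

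**Working it through.** **Inputs from the documents.** Section B (Specific Aims): "Thirty of these participants will be randomly assigned to receive a FitBit Zip™" (n = 30), "or to a control group (n=20". Section C: "participants will be randomly allocated in a 2:1 ratio (intervention: control", which would be about 33 and 17 of 50. Both splits were checked.

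**Not in the documents, so assumed.** Two-sided alpha 5%; no dropout; the size of the walking effect; the item format; the baseline to follow-up correlation; the proportion of controls who increase. The plan states no power calculation, so it has no figure to reproduce.

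**Check 1: formula.** Let change be normal with a shift of d SDs of change, and let p_c be the proportion of controls who increase. Then p_i = Φ(Φ⁻¹(p_c) + d).

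Example with d = 0.8 and p_c = 0.30:
- p_i = Φ(−0.524 + 0.8) = 0.609.
- Pooled p = (30 × 0.609 + 20 × 0.30)/50 = 0.485.
- Null SE = √(0.485 × 0.515 × (1/30 + 1/20)) = 0.144.
- Alternative SE = √(0.609 × 0.391/30 + 0.30 × 0.70/20) = 0.136.
- Chi-square power = Φ((0.309 − 1.96 × 0.144)/0.136), which is 57.5% before rounding.
- A t-test on change has noncentrality 0.8 × √(30 × 20/50) = 2.77 and power 77.5%.
- Loss: 77.5 − 57.5 = 20.0 points.

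Over p_c = 0.20 to 0.50 the loss is 5 to 7 points at d = 0.3, 12 to 17 at d = 0.5 and 19 to 24 at d = 0.8. At 33 versus 17 the example still loses about 20 points.

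**Check 2: simulation with ordinal items.** Baseline b ~ N(0,1); follow-up f = ρb + √(1 − ρ²)e + d·arm. Both are cut at the same points into levels. Here d is in SDs of the follow-up value, not of change. Three analyses were compared: uncorrected chi-square on any increase, Wilcoxon on the ordinal change, and linear regression of follow-up on arm and baseline. For five equal levels, 30 versus 20:

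| ρ | d | Chi-square | Wilcoxon | Adjusted | Gain, Wilcoxon | Gain, adjusted |
|---|---|---|---|---|---|---|
| 0.5 | 0.5 | 23% | 31% | 42% | 8 | 19 |
| 0.5 | 0.65 | 36% | 47% | 64% | 11 | 28 |
| 0.5 | 0.8 | 46% | 61% | 80% | 15 | 34 |
| 0.7 | 0.5 | 32% | 44% | 55% | 12 | 23 |
| 0.7 | 0.65 | 50% | 65% | 77% | 15 | 27 |
| 0.7 | 0.8 | 64% | 80% | 90% | 16 | 26 |

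Type I error at d = 0 was 4.3% to 5.1% for all three. With 4,000 trials each power figure has a standard error of at most √(0.25/4000) = 0.8 points.

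**Check 3: other formats and smaller effects.**
- Three levels, ρ = 0.5, d = 0.65: chi-square 27%, adjusted 57%, a gain of 30.
- Four levels with half of participants in the lowest, ρ = 0.5, d = 0.5: one run gave chi-square 27.7% and Wilcoxon 29.9%, a gain of 2.2, which agrees with about 3 within simulation error.
- Five levels, ρ = 0.5, d = 0.3: chi-square 11.4%, Wilcoxon 14.6%, a gain of 3.2. At d = 0.2: 7.8% and 9.7%, a gain of 1.9.
- Heavy-tailed change (t with 3 df), d = 0.5: chi-square 51%, t-test 48%, Wilcoxon 62%. The gain there comes from ranks, not means.
- With Yates' correction, chi-square power in the five-level scenarios falls from 23–64% to 14–50%. The SAP does not say which version is meant.

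**Gain over uncorrected chi-square, across 3 to 5 levels (the skewed four-level item included) and ρ 0.5 to 0.7:**

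| Shift | Undo the cut (Wilcoxon) | Undo the cut and adjust for baseline |
|---|---|---|
| 0.5 to 0.8 SD | about 3 to 18 points | about 11 to 36 points |
| 0.2 to 0.3 SD | about 1 to 5 points | about 1 to 11 points |

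The adjusted analysis simulated was linear regression. Proportional-odds regression was not simulated.

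**The case against.** The strongest reply has four parts.

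*Walking is not a listed outcome.* The study collects preliminary data and states no power for anything. Physical Function, which is listed, has T-score means and the repeated-measures model, so Aim 2c is served without the walking test. The Background sentence describes CBT in general, whereas this study tests monitoring and reporting. All of this stands, and it limits the importance of the point.

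*The effect size is invented.* Nothing in the documents supports 0.5 to 0.8 SD from six weeks of monitoring, and at 0.2 to 0.3 SD the gain can be 1 or 2 points. This stands. A reader might infer that every real effect costs more than 5 points; that does not hold.

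*The larger gains are not all due to the cut.* Baseline adjustment is a separate choice, and the 11 to 36 points combine the two. This stands, and the two are therefore reported separately.

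*The remedy is still underpowered.* At 0.5 SD with five levels the adjusted analysis reaches only 42% to 55%. This is true, and it is the reason to argue for an estimate and interval rather than for a better significance test.

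A reader might also infer that the SAP ignores the direction of change. It does not: increase versus no increase is kept. What is lost is the size of change and the distinction between a decrease and no change.

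None of this supplies a full-scale walking analysis or a reason for the cut.

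**Conclusion.** The point holds as a modest one. The SAP's only between-arm activity comparison is a dichotomy with no stated rationale and no accompanying analysis on the recorded scale.

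The power gains tabulated above rest on 30 versus 20, two-sided 5%, no dropout, a roughly normal latent scale and a graded item. None of these except the arm sizes comes from the documents, so the ranges are conditional and are not bounds. If the survey itself asked only whether walking had increased, there would be no fuller scale to recover. The wording, which compares baseline with follow-up and separates decreased from the same, points the other way.

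A reader might infer that the cut undermines the trial's main conclusions. The documents do not support that: adherence and Pain Interference are the primary outcomes, and neither depends on the walking test. The main loss is a usable estimate of the walking effect for the later trial.

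**What to change.** In Functional outcomes, replace the walking chi-square with a between-arm comparison of follow-up walk frequency and, separately, follow-up walk duration. Analyse each on its full recorded scale, adjusted for the baseline value of the same item. Use proportional-odds regression, or linear regression if the items are numeric or the categories are too sparse for the ordinal model at about 50 participants. Report the estimate with a 95% confidence interval. Keep increased, same and decreased by arm as a descriptive table. State the items and their response levels so that the choice of model can be followed.

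The cost is a short SAP change and one regression per item, on the baseline and follow-up answers the chi-square already needs. No extra data, visits or participants are required. The small downside is that an odds ratio or mean difference is harder to explain than a percentage, which the descriptive table still provides.

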- *Automatic upload:* As described above, the research assistant will instruct participants in how to set up the FitBit so that data *automatically uploads* to the intervention website. Note that during this set-up process, the devices will be paired with a study account, and the email address provided will belong to the study. The information provided to the Fitbit company during set-up will not be identifying. It will include a study username, a masked birthdate (01/01/birth year plus or minus a constant), and a height and weight that is the male or female average, as appropriate.

*Control group:* Control group members will not track their steps during the study period, but will participate in baseline and follow-up data collection, after which they will receive a FitBit to keep.

Data collection:

Data will be collected via telephone by a trained research assistant at baseline and following the 6-week intervention.

Measures:

*Primary outcomes:*

Adherence to reporting will be indicated by the proportion of days with successfully logged step-counts, i.e., reported days/14 total days for each of the three reporting modes.

Pain interference: 4-item subscale from the PROMIS-29 Adult Profile, measured at baseline and follow-up.

*Secondary outcomes:*

Physical functioning: 4-item subscale from the PROMIS-29 Adult Profile, measured at baseline and follow-up.

Social participation: 4-item subscale from the PROMIS-29 Adult Profile, measured at baseline and follow-up.

Validity of manually-reported step counts will be assessed by comparing up to one month of IVR or SMS- collected data to data collected by syncing the device. Validity of the data will also be

assessed by examining associations between step data and relevant baseline characteristics (e.g., functioning scores, comorbidities, and age).

*Other baseline survey measures* (to characterize sample and/or as potential moderators of adherence and outcomes): *Demographics and health*: age, gender, education, race/ ethnicity, marital status, health literacy, comorbidities, cognitive functioning, physical activity. *Pain-related*: pain duration, number and location of pain sites, pain treatments, pain centralization. *Technology-related*: attitudes toward technology, eHealth literacy, social support for technology use.

*Staff burden*: Number of participant calls to the study technical support line, time spent giving technical assistance, and difficulties encountered as described in staff notes.

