*Satisfaction/Acceptability*. In the follow-up survey, intervention group participants will be asked a series of Likert scale items about their experience with the trackers and reporting modes.

Open-ended items for intervention participants will assess challenges and facilitators for device and reporting method use; identify environmental and individual barriers to using devices; and obtain feedback on how program implementation might be improved for this particular population.

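### The SAP tests between-arm change in low-intensity walking, but the protocol specifies no walking measure at follow-up, lists no walking outcome, and leaves the responder definition ambiguous

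*Combined protocol and SAP*

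**What the plan says.** In the Statistical Analysis Plan, under *Functional outcomes*, the test is introduced with "We used chi-square tests to evaluate differences in the proportion of participants in intervention vs control groups". It is applied to two things: reaching a 3-point change on PROMIS Pain Interference, and having "increased the frequency and duration of their low-intensity walks from baseline to follow-up (vs decreased or stayed the same").

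Section C (Methods), *Measures*, names adherence and pain interference as primary outcomes. The secondary outcomes are physical functioning, social participation and the validity of manually reported step counts. Walking is in neither list. Physical activity appears once, under *Other baseline survey measures*, in the run "health literacy, comorbidities, cognitive functioning, physical activity". The stated purpose of that list is "to characterize sample and/or as potential moderators of adherence and outcomes".

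Each PROMIS subscale, by contrast, is described as a "4-item subscale from the PROMIS-29 Adult Profile, measured at baseline and follow-up". On timing in general, section C says: "Data will be collected via telephone by a trained research assistant at baseline and following the 6-week intervention". The follow-up content it describes beyond PROMIS is a question about future contact, open-ended items for the intervention arm, and a satisfaction block in which "intervention group participants will be asked a series of Likert scale items about their experience with the trackers and reporting modes". No walking item or instrument is named anywhere.

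**The concern.** A test of change needs the same measure at both time points in both arms. The protocol specifies such a pair for the PROMIS subscales but not for walking. Someone building the follow-up questionnaire from the Measures section alone would leave walking out, and the test would then have no follow-up value.

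If the item is collected anyway, the result is a between-arm comparison on an outcome with no stated tier and no fixed definition. That matters more for walking than for most measures. The intervention is step tracking, participants know whether they have a tracker, and any walking measure common to both arms would have to be self-reported. The study is meant to inform a later trial, so a walking difference that depends on an unstated classification rule could mislead that design.

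**Working it through.** **1. Is there a scheduled follow-up value?** No figure in the plan can be reproduced here, so the check sets the sections side by side.

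| Item | Baseline | Follow-up | Outcome tier |
|---|---|---|---|
| Three PROMIS subscales | specified | specified | primary or secondary |
| Physical activity | specified | not specified | none (descriptor or moderator) |
| Low-intensity walk frequency and duration | not named | not named | none |

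Device data cannot substitute. Controls do not track steps during the study and receive a device only after the follow-up survey. The intervention arm receives the device after the baseline survey and randomization, so it has no device baseline either.

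**2. Does the split classify everyone?** Frequency and duration can each go up, stay the same or go down, giving 3 × 3 = 9 patterns.

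- Both up: 1 pattern, in the first category.
- Neither up: 2 × 2 = 4 patterns, in the second category.
- Exactly one up: 9 − 1 − 4 = 4 patterns (up/same, up/down, same/up, down/up), in neither category on the literal joint reading.

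If frequency and duration are tested separately, 0 patterns are unclassified. The 4 of 9 counts patterns, not people; the documents give no frequencies.

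**3. How much could the unstated rule matter?** This is a hypothetical data set, for scale only. It uses the arm sizes in Specific Aim 1 (30 intervention, 20 control). Suppose 12 and 4 rise on both components, and 3 and 6 rise on only one.

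| Rule for those who rise on one component | Intervention | Control | Difference | Chi-square p (uncorrected) |
|---|---|---|---|---|
| Count as not increased | 12/30 = 40.0% | 4/20 = 20.0% | 20.0 points | 0.137 |
| Exclude | 12/27 = 44.4% | 4/14 = 28.6% | 15.8 points | 0.323 |
| Count as increased | 15/30 = 50.0% | 10/20 = 50.0% | 0 points | 1.0 |

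**4. How many between-arm outcome tests are there?** The SAP has three PROMIS time-by-treatment tests, one Pain Interference responder test, and walking as one test or two. It states no significance level and no multiplicity rule. At an assumed 5% per test, and if the tests were independent:

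- Walking as one endpoint, five tests: 1 − 0.95^5 = 0.226, about 23%.
- Walking as two endpoints, six tests: 1 − 0.95^6 = 0.265, about 26%.

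Both figures are too high for this plan, because the tests overlap; the Pain Interference responder test, for example, uses the same score as one of the ANOVAs. The 4-of-9 count belongs only to the joint reading and the 26% only to the separate reading, so they must not be quoted together.

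**5. What could the test detect?** With 30 and 20 participants, an assumed two-sided 5% level and assumed control rates of 0.2 to 0.4, 80% power needs a difference of about 39 to 40 percentage points.

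**The case against.** The strongest reply is that the protocol does not limit walking to baseline. Its general sentence on data collection covers both calls without saying which items are repeated, and the SAP's own wording presupposes a follow-up value. A reader might infer from the Measures section that the analysis cannot be done; the documents do not support that. What stands is narrower: no follow-up walking item is specified, and listing physical activity as a baseline measure points away from one.

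A reader might also infer that the walking test lies outside the aims. Aim 2c compares change in functional outcomes between the arms, and the SAP places the walking test under that heading. Walking is not named in the aim, but it is not foreign to it.

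A third tempting inference is that the past tense shows the test was chosen after the data were seen. The same tense is used in that section for PROMIS scoring, the interaction term, the Pain Interference responder test and the qualitative coding, so it says nothing particular about walking.

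On the split, the bracketed wording may be shorthand for everyone who did not increase, or two separate tests may have been meant. Either would remove the gap, but the SAP does not say which applies. Finally, this is a study to gather preliminary data, and nothing in the documents claims efficacy from walking. That limits the consequence but leaves the endpoint undefined.

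**Conclusion.** The point holds as a mismatch between the Measures section and the SAP, together with an ambiguous endpoint. The SAP's walking test relies on a follow-up measurement that the protocol does not specify, for an outcome it does not list, and device data cannot supply it.

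The size depends on the reading. On the joint reading, 4 of 9 change patterns have no category, and in the hypothetical example the difference between arms runs from 20 points to 0 according to the rule chosen. On the separate reading, everyone is classified and the cost is one more unadjusted test, taking the false-positive bound from about 23% to about 26%. These bounds assume 5% per test and independence; the true chance is lower by an amount the documents do not allow one to calculate. The share of participants who would rise on only one component is also unknown.

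This should be corrected, but it does not affect the two primary outcomes. The documents do not show that the analysis is impossible or that it was added after the fact.

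**What to change.** **In section C, Measures:** name the walking frequency and duration items, schedule the same items at baseline and follow-up in both arms, and list walking as an exploratory, self-reported outcome.

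**In the SAP, Functional outcomes:**
- State whether frequency and duration form one endpoint or two.
- Compare the follow-up value between arms, adjusted for its baseline value. Use weekly walking time (frequency × duration) if the items are numeric, or an ordinal model if they are response categories. The documents do not give the response format, so this choice has to follow the instrument.
- If a responder split is kept, make it exhaustive: increased, yes or no, with a stated rule for participants who rise on one component only.
- State that the walking result is exploratory and does not support an efficacy claim.

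**Cost:** a slightly longer follow-up call, some SAP wording, and an exploratory label on the result. If follow-up is already complete, the remedy is to report which walking items were collected and when, the classification rule used, and the exploratory status.
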